6.2.2 Ixazomib Destruction

Ixazomib (expired or end of study) should be destroyed on site according to the institution's standard operating procedure. Be sure to document removal and destruction on drug accountability logs.

6.3 Lenalidomide

6.3.1 Administration of Lenalidomide

After first two 28 day cycles of ixazomib, the starting dose of lenalidomide will be 10 mg po daily on days 1-28, every 28 day cycles for two cycles alternating with ixazomib. Lenalidomide should be taken orally about the same time every day, either with or without food. The capsules should not be opened, broken or chewed.

6.3.2 How Supplied

Lenalidomide is commercially available. Patients, prescribers and dispensing pharmacies must be registered in the FDA-mandated Revlimid REMS TM program.

6.4 Dose-Modification Guidelines

6.4.1 Recommended Ixazomib Criteria for Beginning or Delaying a Subsequent Treatment Cycle & Dose Modifications for Treatment Associated Toxicity

Treatment with ixazomib will use a cycle length of 28 days. For a new cycle of treatment to begin, the patient must meet the following criteria:

- ANC must be $\geq 1,000/\text{mm}^3$.
- Platelet count must be $\geq 75,000/\text{mm}^3$.
- All other nonhematologic toxicity (except for alopecia) and peripheral neuropathy must have resolved to \leq Grade 1 or to the patient's baseline condition.

If the patient fails to meet the above-cited criteria for initiation of the next cycle of treatment, dosing should be delayed for 1 week. At the end of that time, the patient should be re-evaluated to determine whether the criteria have been met. If the patient continues to fail to meet the above-cited criteria, delay therapy and continue to reevaluate. The maximum delay before treatment should be discontinued will be 30 days or at the discretion of the Principal Investigator.

For dosing recommendations upon recovery, refer to Table 6-1, Table 6-2, and Table 6-3.

**Fred Hutchinson Cancer Research Center
Clinical Study Protocol [FHCRC 9266]**

Table 6-1 Ixazomib Dose Adjustments

Dose Level	Dose (mg)
Starting Dose	4.0 mg
-1	3.0 mg
-2	2.3 mg
-3	Discontinue

Dosing adjustments for hematologic toxicity are outlined in Table 6-2.

Table 6-2 Ixazomib Dose Adjustments for Toxicities

Criteria	Action
Within-Cycle Dose Modifications	
• If platelet count $\leq 30 \times 10^9/L$ or ANC $\leq 0.50 \times 10^9/L$ on a ixazomib dosing day (other than Day 1)	
• Ixazomib dose should be withheld.• Complete blood count (CBC) with differential should be repeated at least every other day until the ANC and/or platelet counts have exceeded the prespecified values (see Section 6.4.1) on at least 2 occasions.• Upon recovery, ixazomib may be reinitiated with 1 dose level reduction.
Dose Modifications for Subsequent Treatment Cycles	
• Delay of up to 4 weeks in the start of a subsequent cycle due to lack of toxicity recovery as defined in Section 6.4.1. • ANC $< 1.0 \times 10^9/L$, platelet count $< 75 \times 10^9/L$, or other nonperipheral neuropathy, nonhematologic toxicities (except for alopecia) $>$ Grade 1 or not to the patient's baseline condition	
• Hold ixazomib until resolution as per criteria Section 6.4.1.• Upon recovery, reduce ixazomib 1 dose level.• The maximum delay before treatment should be discontinued will be 30 days or at the discretion of the PI.
Dose Modifications for Subsequent Treatment Cycles	

Table 6-2 Ixazomib Dose Adjustments for Toxicities

Criteria	Action
• All hematologic toxicities	
 • For hematologic toxicity that occurs during a cycle but recover in time for the start of the next cycle: 
 ○ If dose was reduced within the cycle, start the next cycle at that same dose. ○ If due to toxicity timing, i.e., after Day 15 dosing thus a dose reduction was not required at that point in the cycle, reduce ixazomib by 1 dose level at the start of that cycle. ○ Do not reduce the dose both within a cycle and at the start of the cycle for the same most severe toxicity.

Treatment modifications due to ixazomib-related AEs are outlined in Table 6-3.

Table 6-3 Ixazomib Treatment Modification (Delays, Reductions, and Discontinuations) Due to Adverse Events (Non-Hematologic Toxicities)

Adverse Event (Severity)	Action on Study Drug	Further Considerations
Peripheral Neuropathy: Grade 1 peripheral neuropathy	No action	Grade 1 signs and symptoms: asymptomatic; without pain or loss of function; clinical or diagnostic observations only ^[7]
New or worsening Grade 1 peripheral neuropathy with pain or Grade 2	Hold ixazomib until resolution to Grade ≤ 1 without pain or baseline	Grade 2 signs and symptoms: Moderate symptoms; limiting instrumental activities of daily living (ADL) ^[7]
New or worsening Grade 2 peripheral neuropathy with pain or Grade 3	Hold ixazomib until resolution to Grade ≤ 1 without pain or baseline Reduce ixazomib to next lower dose upon recovery	Grade 3 signs and symptoms: severe symptoms; limiting self-care ADL; assistive device indicated ^[7]

Table 6-3 Ixazomib Treatment Modification (Delays, Reductions, and Discontinuations) Due to Adverse Events (Non-Hematologic Toxicities)

Adverse Event (Severity)	Action on Study Drug	Further Considerations
New or worsening Grade 4 peripheral neuropathy	Discontinue ixazomib	
Grade 2 Rash	Symptomatic recommendations as per section 6.10	At the discretion of the investigator, may require dose modification.
Grade 3 Nonhematologic, nonperipheral neuropathy toxicity judged to be related to ixazomib	Hold ixazomib until resolution to Grade < 1 or baseline	Symptomatic recommendations noted in Section 6.10
If not recovered to < Grade 1 or baseline within 30 days	Reduce ixazomib to next lower dose upon return to < Grade 1 or baseline	
Subsequent recurrence Grade 3 that does not recover to < Grade 1 or baseline within 30 days	Hold ixazomib until resolution to Grade < 1 or baseline	
Grade 4 Nonhematologic nonperipheral neuropathy toxicities judged to be related to ixazomib	Consider permanently discontinuing ixazomib	Exceptions are cases in which the investigator determines the patient is obtaining a clinical benefit

Once ixazomib is reduced for any toxicity, the dose may not be re-escalated.

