Symptomatic measures such as antihistamines or corticosteroids (oral or topical) have been successfully used to manage rash and have been used prophylactically in subsequent cycles. The use of a topical, IV, or oral steroid (e.g., prednisone \leq 10 mg per day or equivalent) is permitted. Management of a Grade 3 rash may require intravenous antihistamines or corticosteroids. Administration of ixazomib or lenolidamide should be modified per protocol and re-initiated at a reduced level from where rash was noted (also, per protocol).

In line with clinical practice, dermatology consult and biopsy of Grade 3 or higher rash or any SAE involving rash is recommended. Prophylactic measures should also be considered if a patient has previously developed a rash (e.g., using a thick, alcohol-free emollient cream on dry areas of the body or oral or topical antihistamines). A rare risk is Stevens-Johnson Syndrome, a severe and potentially life-threatening rash with skin peeling and mouth sores, which should be managed symptomatically according to standard medical practice. Punch biopsies for histopathological analysis are encouraged at the discretion of the investigator.

Thrombocytopenia

Blood counts should be monitored regularly as outlined in the protocol with additional testing obtained according to standard clinical practice. Thrombocytopenia may be severe but has been manageable with platelet transfusions according to standard clinical practice. Ixazomib and lenalidomide administration should be modified as noted as per dose modification recommendations in the protocol when thrombocytopenia occurs (see Table 6-2). Therapy can be reinitiated at a reduced level upon recovery of platelet counts. A rare risk is thrombotic thrombocytopenic purpura (TTP), a rare blood disorder where blood clots form in small blood vessels throughout the body characterized by thrombocytopenia, petechiae, fever, or possibly more serious signs and symptoms. TTP should be managed symptomatically according to standard medical practice.

Neutropenia

Fred Hutchinson Cancer Research Center
Clinical Study Protocol [FHCRC 9266]

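### For non-hematologic toxicity, the ixazomib rules disagree on restart dose, recovery grade and the 30-day limit, and Section 6.4.1 does not say which table governs

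*Combined protocol and SAP*

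**What the plan says.** Section 6.4.1 sets the conditions for starting a cycle. On non-hematologic toxicity it reads "All other nonhematologic toxicity (except for alopecia) and peripheral neuropathy must have resolved to" Grade 1 or lower, or baseline. If the conditions are not met the cycle is delayed, for at most 30 days unless the Principal Investigator decides otherwise. The section then says "For dosing recommendations upon recovery, refer to Table 6-1, Table 6-2, and Table 6-3", without an order among the tables.

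Table 6-2 is introduced with "Dosing adjustments for hematologic toxicity are outlined in Table 6-2". Its title, however, refers to toxicities in general, and its row on delayed cycles includes "other nonperipheral neuropathy, nonhematologic toxicities (except for alopecia") above Grade 1. The action there is to hold until the 6.4.1 criteria are met and then go down one dose level.

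Table 6-3 covers Grade 3 non-hematologic, non-neuropathy toxicity judged related to ixazomib. Its action is "Hold ixazomib until resolution to Grade < 1 or baseline". The next row applies if recovery has not occurred within 30 days, and says "Reduce ixazomib to next lower dose upon return to < Grade 1 or baseline". A note below the table rules out re-escalation.

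Section 6.10 says that after rash, ixazomib or lenalidomide is to be "re-initiated at a reduced level from where rash was noted", followed by a parenthesis referring back to the protocol. Section 6.4.2 repeats the Grade 1 or lower condition for lenalidomide cycles, while the Grade 3 rows of Table 6.5 hold until below Grade 1 or baseline. Section 6.15 lists inability to resume more than 30 days after stopping for toxicity among the reasons for withdrawal.

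**The concern.** An investigator with one patient in front of them can follow the plan faithfully and reach two different restart doses, and in some cases two different answers on whether the patient may restart at all. Because reductions are permanent, the choice carries through every later ixazomib cycle and bears on the secondary objective of delivering the planned therapy.

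It can also reach the primary endpoint. The Protocol Summary counts toward the toxicity stopping rule those patients who do not recover and resume within 30 days. Whether a patient has recovered depends on the recovery grade used, and the plan prints two.

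**Working it through.** No sample size, power or error rate enters here. The check is to apply each rule to the same patients. Baseline is Grade 0 and the toxicity is non-hematologic and not neuropathy.

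| Patient | 6.4.1 and Table 6-2 | Table 6-3 |
|---|---|---|
| A. Related Grade 3, above Grade 1 on planned Day 1, fully resolved 10 days later | Delay, then one level down | Hold; no reduction stated, since recovered within 30 days |
| B. Grade 2 on planned Day 1, resolved one week later | Delay, then one level down | No general Grade 2 row (only rash, left to the investigator) |
| C. Related Grade 3 mid-cycle, fully resolved before the next Day 1 | Not triggered | Hold; no reduction stated |
| D. Related Grade 3, down to Grade 1 on planned Day 1 | 6.4.1 met; cycle may start | Still on hold |
| E. Related Grade 3, settled at Grade 1 for more than 30 days | 6.4.1 met; cycle may start | Held past 30 days; reduced dose once resolved |

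**Dose on restart.** Patient A falls under both tables and gets different doses. This does not depend on the recovery-grade symbol, because the event has fully resolved. Comparing B with C, a Grade 2 event can cost a dose level while a Grade 3 event does not; the difference comes from timing relative to Day 1. Section 6.10 adds a third statement for rash: a reduced level on restart, without the 30-day condition in Table 6-3.

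**Recovery grade.** D and E differ only through the sign: at or below Grade 1 in 6.4.1 and 6.4.2, below Grade 1 in the Grade 3 rows of Tables 6-3 and 6.5. If baseline is Grade 1, both conditions are met at Grade 1 and the difference disappears. Exclusion criterion 2 allows patients to enter with residual Grade 1 toxicity, so some will be in that position.

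**Thirty days.** Table 6-3 provides for a reduced-dose restart after more than 30 days without recovery. Section 6.4.1 makes 30 days the point of discontinuation (subject to the Principal Investigator), and 6.15 makes it a reason for withdrawal.

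**Size for one patient.** Inputs are the dose levels in Table 6-1 (4.0, 3.0, 2.3 mg, then discontinue), the flow chart (12 of 24 cycles are ixazomib) and three doses per ixazomib cycle.

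- First reduction: (4.0 − 3.0)/4.0 = 25%. Second: (3.0 − 2.3)/3.0 = 23.3%. At 2.3 mg the next step is discontinuation.
- Planned ixazomib over 24 cycles: 12 × 3 × 4.0 = 144 mg. With one reduction from Cycle 2: (1 × 3 × 4.0) + (11 × 3 × 3.0) = 12 + 99 = 111 mg, a shortfall of 33/144 = 22.9%.
- Over the first 12 cycles (six with ixazomib): planned 6 × 12 = 72 mg; with the same reduction 12 + (5 × 9) = 57 mg, or 79.2%. One reduction alone therefore leaves a patient above half of planned ixazomib, if the feasibility rule in 7.1.8 is counted in milligrams, which it does not specify.

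**The case against.** The best defense is that the tables are cumulative. Section 6.4.1 cites them together; Table 6-3 can be read as adding a stricter hold for a more severe event, and its Grade 3 row is silent on restart dose rather than telling the reader to resume unchanged. On that reading patient A is simply reduced under Table 6-2. This is a possible reading, but the text does not state it, and it leaves the 30-day condition for reduction in Table 6-3 with no clear role when a cycle is delayed. Nor does the hematologic lead-in to Table 6-2 settle matters, since the row names non-hematologic toxicity.

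A reader might infer that the plan systematically penalizes milder toxicity, or that the rules are opposites that nobody could have intended. The documents do not support that. At the same timing, a Grade 3 event meets the Table 6-2 trigger just as a Grade 2 event does; the inversion needs different timing, or Table 6-3 read alone. Persistence into the next cycle could be a deliberate basis for reduction.

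The point on Section 6.10 is limited by its parenthesis, which sends the reader back to the protocol's own rules. The mismatch stands, but 6.10 is not an independent rule.

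The recovery-grade point rests on one symbol, and a lost underline would turn one sign into the other. Against that, the stricter sign recurs in the Grade 3 rows of both drugs' tables, while the looser one is printed in their neuropathy rows.

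Finally, the 30-day limit in 6.4.1 yields to the Principal Investigator, and 6.15 is worded as the investigator's right to withdraw a patient. Section 7.1.7 describes the stopping rule by Grade IV toxicity and does not mention the 30-day failure; only the Protocol Summary does. So an effect on the stopping count is possible, not certain.

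**Conclusion.** The point stands as a conflict in the rules as written. For a related Grade 3 event that delays an ixazomib cycle and resolves within 30 days, the plan yields 4.0 or 3.0 mg depending on the table followed, and the lower dose is permanent. This conclusion needs only the absence of stated precedence. The restart-dose conflict concerns ixazomib only, because lenalidomide Table 6.4 has no non-hematologic row. The recovery-grade conflict concerns both drugs, assumes the printed symbol is correct, and matters only when baseline is Grade 0 and toxicity has fallen to Grade 1.

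Under the Protocol Summary's definition, reclassifying one patient could matter: the boundaries in 7.1.7 are small, and a third withdrawal among ten reaches the 3/10 limit. A reader might go further and infer that the stopping rule's stated operating characteristics are wrong, or that the conflict will be frequent because Table 1-2 reports nausea and diarrhea at 47%, fatigue at 45% and rash at 40%. Neither follows. No operating characteristic depends on these tables, and the rates cover all grades rather than Grade 3 events or toxicity present on Day 1. The frequency of conflicting cases is unknown.

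**What to change.** The sponsor-investigator should reconcile 6.4.1, 6.4.2, Tables 6-2, 6-3 and 6.5, 6.10 and 6.15 so that:

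- each non-hematologic toxicity has one recovery grade and one restart action;
- the text states which table governs when more than one applies, and the lead-in to Table 6-2 matches its contents;
- the restart after 30 days in Table 6-3 and the 30-day limits in 6.4.1 and 6.15 agree;
- the recovery-grade symbol is checked against the source and made uniform where uniformity is meant;
- the same recovery grade is used to classify the 30-day failure-to-resume event.

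The choice of rules belongs to the investigators, and no view is given here on which is right. The cost is amendment wording; sample size and stopping boundaries are unaffected. For patients already treated, recording which table was followed at each restart would allow delivered dose and 30-day events to be interpreted.

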Hypothesis of this phase II study is that ixazomib and lenalidomide as maintenance therapy after autologous PBSC transplant for Multiple Myeloma will be safe and tolerable and prolong the time to disease progression post transplant. The treatment regimen is alternating ixazomib with lenalidomide every two months until disease progression, intolerable toxicity or maximum of 24 months of therapy. The dose of ixazomib is 4.0 mg po on days 1, 8 and 15 per each 28-day cycle given for two consecutive months, followed by then lenalidomide 10 mg po daily for two consecutive months, then ixazomib for two months etc. Dose reduction for toxicity will be incorporated. If >30 days off initially planned next cycle of therapy, then patient will be taken off study. Toxicity will be graded per CTCAE version 4.0. The first four months of therapy will be used as the time period to evaluate end point of toxicity for stopping rules. Toxicity that meets stopping rules will be determined based on the number of patients that are withdrawn from study for significant toxicity (grade IV, non-hematological, non-metabolic, non-peripheral neuropathy) and the number of patients who stop therapy for toxicity and are withdrawn from study as they could not recover adequately and resume therapy by 30 days from the initial stopping of the study drugs. We shall consider the withdrawal rate to be excessive, and hence the therapy to be too toxic, if the true withdrawal rate from the study exceeds 15% in the first four months. An interim analysis at 15 treated patients will be conducted. If > 50% of patients are unable to receive > 50% of planned therapy in first 12 months of treatment, the study will be terminated due to lack of feasibility. Another endpoint is time to disease progression. Patients will be followed for initial response and for progression of disease, response criteria will be determined by International Myeloma working group criteria. In patients with chemo-refractory disease at the time of ASCT, the therapy will be felt to be promising if median time to progression is >9 months. If chemo-sensitive disease at time of ASCT, the therapy will be felt to be promising if median time to progression is >41 months based on CALGB 10014 lenalidomide maintenance study post ASCT. Cytogenetic information will be collected and initial response rates and outcome will be descriptively reported. Patients will be followed for overall survival. The incidence of secondary cancers will also be collected. If this study regimen is deemed to be potentially efficacious and is not regarded as too toxic per stopping rules outlined above and observed EFS rate are consistent with rates that match or exceed historical benchmarks, then a phase III trial to show efficacy rate of this regimen over single agent therapy will be designed.

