Rash Grade 2	Symptomatic recommendations as per Section 6.10	At the discretion of the investigator, may require dose modification.	
Grade 3 nonhematologic, nonperipheral neuropathy toxicity judged to be related to lenalidomide	Hold study drug until resolution to Grade < 1 or baseline	Symptomatic recommendations noted in Section 6.7	
If not recovered to $<$ Grade 1 or baseline within 30 days	Reduce study drug 1 to next lower dose upon return to $<$ Grade 1 or baseline		
Subsequent recurrence Grade 3 that does not recover to $<$ Grade 1 or baseline within 30 days	Hold study drug until resolution to Grade < 1 or baseline Reduce study drug to next lower dose	Monitor closely, take appropriate medical precautions, and provide appropriate symptomatic care	
Grade 4 nonhematologic, nonperipheral neuropathy toxicities judged to be related to lenalidomide	Consider permanently discontinuing lenalidomide	Exceptions are cases in which the investigator determines the patient is obtaining a clinical benefit	

**Fred Hutchinson Cancer Research Center
Clinical Study Protocol [FHCRC 9266]**

Once lenalidomide is reduced for any toxicity, the dose may not be re-escalated.

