6.15 Termination of Treatment and/or Study Participation

Patients will be informed that they have the right to withdraw from the study at any time for any reason, without prejudice to their medical care. The investigator also has the right to withdraw patients from the study for any of the following reasons:

- Adverse event
- Protocol violation
- Lost to follow-up
- Progressive disease
- Study terminated
- The treatment appears detrimental in the judgment of primary physician

**Fred Hutchinson Cancer Research Center
Clinical Study Protocol [FHCRC 9266]**

- They develop non-hematological, non-metabolic, non-peripheral neuropathy grade IV toxicity
- They are unable to resume therapy more than 30 days after initial stopping of therapy for toxicity or cannot tolerate lowest dose reduction level
- Repeated noncompliance to protocol in view of principal investigator

Patients who are withdrawn from the study will not be replaced.

At the time of withdrawal, all study procedures outlined for the End of Study visit should be completed per study calendar (See Study Flow Chart). The primary reason for patient's withdrawal from the study should be recorded in the source documents and CRF.

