7.1.7 Safety Analysis

The first endpoint is to evaluate the toxicity of the proposed therapy. The first four months of therapy will be used as the time period in which toxicity will be evaluated and stopping rules for unacceptable toxicity will be implemented. Rules for stopping therapy will be based on rate of withdrawal due to significant toxicity (grade IV, non-hematological, non-metabolic and non-peripheral neuropathy). A true withdrawal rate within first 4 months of 15% will be considered excessive. Withdrawal rate will be assessed after every ten patients are treated. Enrollment will not be held though until the 10th patient enrolled becomes evaluable. Sufficient evidence will be taken for a lower limit to the corresponding one sided 80% confidence interval that exceeds 15%. Operationally observed rates that say regimen is too toxic would be 2/5, 3/10, 4/15, 5/20, 6/25 and 7/30. If the true probability of withdrawal from the study is 5%, the probability of deeming this regimen as too toxic after 15 or 30 patients have been treated is approximately .03 and .03, respectively. If the true probability of withdrawal is 10%, these probabilities are approximately .13 and .15, respectively. On the other hand, if the true probability of withdrawal is .30, then the probability of judging this regimen as too toxic after 15 or 30 patients is approximately .78 and .91, respectively.

With the semi-continuous monitoring of the withdrawal rate, the estimate of this rate, should the study run to completion, will be biased slightly downward. Without consideration of this bias, 30 patients will allow us 80% confidence that the estimated withdrawal rate will be within approximately .094 of the true rate under the assumption that the true rate is 20%. The incidence of second cancers will also be collected.

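### The primary stopping rule counts withdrawals, yet withdrawal for grade IV toxicity is discretionary and the 30-day event is defined inconsistently, so the count can understate toxicity

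*Combined protocol and SAP*

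**What the plan says.** **What is counted.** Section 7.1.7 states: "Rules for stopping therapy will be based on rate of withdrawal due to significant toxicity (grade IV, non-hematological, non-metabolic and non-peripheral neuropathy". The synopsis (Protocol Summary, Overview of Study Design) counts "the number of patients that are withdrawn from study for significant toxicity (grade IV, non-hematological, non-metabolic, non-peripheral neuropathy". It adds a second route, which 7.1.7 omits: patients who stopped for toxicity and "could not recover adequately and resume therapy by 30 days from the initial stopping of the study drugs".

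**When a patient is withdrawn for grade IV toxicity.** Section 6.15 opens its list with "The investigator also has the right to withdraw patients from the study for any of the following reasons", and one item is "They develop non-hematological, non-metabolic, non-peripheral neuropathy grade IV toxicity". For related grade 4 non-hematologic, non-neuropathy events, Table 6-3 only asks the investigator to consider stopping ixazomib, and Table 6.5 reads "Consider permanently discontinuing lenalidomide". Both rows carry the exception "Exceptions are cases in which the investigator determines the patient is obtaining a clinical benefit". For grade 4 neuropathy the same tables give a plain instruction to discontinue.

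**The 30-day limit.**
- Removal is mandatory in the synopsis, 4.1 and 6.1. It is subject to Principal Investigator discretion in 6.4.1, Table 6-2 and 6.4.2, and a right in 6.15.
- The clock starts when drug is first stopped (synopsis stopping rule, 6.15) or at the planned next cycle (synopsis off-study rule, 4.1, 6.1, 6.4.2).
- No order of precedence is given.

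**Looks.** Section 7.1.7 says "Withdrawal rate will be assessed after every ten patients are treated" but lists boundaries at every 5 patients: 2/5, 3/10, 4/15, 5/20, 6/25 and 7/30.

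**The concern.** Toxicity is the only primary endpoint (3.1), and this is its only numerical decision rule. The same grade IV event can score 1 or 0 according to an investigator's treatment decision in an open-label, single-arm trial. Keeping a patient on can remove an event from the count but never add one, so any error relative to the toxicity that occurred is downward. No bad faith is needed, because the tables expressly allow a benefiting patient to continue the drug.

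The 30-day wording is a second source of ambiguity. Two people applying the protocol to the same patients could reach different counts, depending on whether they follow the synopsis or 7.1.7 and which clock they use. At stake is whether accrual stops when qualifying toxicity is well above the 15% limit.

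**Working it through.** **Inputs.** From 7.1.7: the six boundaries, a 15% limit, and stated probabilities of stopping after 15/30 patients of .03/.03, .13/.15 and .78/.91 at true withdrawal rates of 5%, 10% and 30%. Assumed, because the documents do not give it: the share *f* of grade IV qualifying patients who are kept on and never counted.

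**Step 1: reproduce the plan's figures.** Exact binomial recursion: add patients one at a time at counted rate *q*, and remove the probability at or above the boundary at each look.

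| Rate | Looks every 5, by 15 / 30 | Looks every 10, by 30 |
|---|---|---|
| .05 | .030 / .031 | .013 |
| .10 | .129 / .146 | .096 |
| .30 | .775 / .912 | .892 |

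The stated figures match looks every 5. The every-ten schedule in the text does not give them. That mismatch is a separate matter; both schedules are carried below so that nothing depends on it.

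**Step 2: effect of retention at a true 30% qualifying rate.**
- (a) 7.1.7 definition, every event grade IV: *q* = .30 × (1 − *f*).
- (b) Synopsis definition, assuming half the events are grade IV and only those can be retained: *q* = .30 × (1 − 0.5*f*).

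Probability of stopping by 30 patients:

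| *f* | (a) *q* | every 5 | every 10 | (b) *q* | every 5 | every 10 |
|---|---|---|---|---|---|---|
| 0 | .300 | .912 | .892 | .300 | .912 | .892 |
| 10% | .270 | .848 | .817 | .285 | .883 | .858 |
| 25% | .225 | .701 | .650 | .2625 | .828 | .794 |
| 1/3 | .200 | .594 | .532 | .250 | .790 | .751 |
| 50% | .150 | .354 | .285 | .225 | .701 | .650 |

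**Step 3: retained patients withdrawn later.** If half of those retained are withdrawn for toxicity later within the four months (assumption), (a) becomes *q* = .30 × (1 − 0.5*f*). At *f* = 1/3, *q* = .25 and the chance of stopping is .790, not .594. At *f* = 50%, *q* = .225 and it is .701, not .354 (looks every 5).

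**Step 4: the two clocks.** For a dose held on day *s* of a 28-day cycle, the initial-stopping limit is day *s* + 30. The planned-next-cycle limit is day 29 + 30 = 59. The gap is 29 − *s* days: 21 for a day 8 hold (day 38 against day 59) and 14 for a day 15 hold (day 45 against day 59). If the interruption begins at the planned cycle start (*s* = 29), the gap is zero. The effect on the count was not modelled.

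**The case against.** The strongest reply is that a withdrawal rate is what the plan chose to monitor. The 15% limit, the boundaries and the probabilities all refer to it, and toxicity-driven withdrawal is a coherent measure of tolerability. This stands: the figures are not wrong for what they describe. They would give the chance of stopping for a given toxicity rate only if every qualifying toxicity led to withdrawal, which the protocol does not require.

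Second, the lead-in to 6.15 covers a generic list that also includes disease progression, which ends treatment elsewhere, and its grade IV item repeats the stopping-rule category. It may have been meant as a removal criterion. Tables 6-3 and 6.5 concern one drug and events related to it, not study withdrawal. Both points are fair, but nothing makes the withdrawal mandatory or counts an event in a patient who stays.

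Third, a reader might infer that a patient with grade IV toxicity can simply carry on uncounted. The documents do not support that. Sections 6.4.1 and 6.4.2 require recovery to grade 1 or baseline before a new cycle, the 30-day limit may remove the patient, and later withdrawal for toxicity within the four months would count. The uncounted group is mainly those who recover in time and are kept on. Serious adverse event reporting (8.2) and independent monitoring (section 10) keep such events visible, but neither makes them stopping-rule events.

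**Conclusion.** The point holds as a gap in the event definition, with a downward-only effect of unknown size. The textual findings are firm: withdrawal for the listed grade IV toxicity is discretionary, retained cases are not counted, and the 30-day event differs between sections in inclusion, force and clock.

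The size rests on the assumed retained share. At a true 30% rate and looks every 5, retention of 10% to 25% lowers the chance of stopping by 30 patients from .91 to .88–.83 if half the events are grade IV, or to .85–.70 if all are. It is lower still with more retention, and closer to .91 if retained patients are later withdrawn. If few are retained, the effect is small.

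A reader might infer that the stated operating characteristics are wrong, or take the .35 in the table as the rule's expected performance. Neither follows. The first reproduces for the withdrawal rate with looks every 5. The second needs half of all qualifying patients retained, every event grade IV and no later withdrawal, and the documents support none of these as an expectation. This is a cheap improvement that should be made.

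**What to change.** Use one event definition in the synopsis and 7.1.7. Within the first four months, count either (i) a grade IV non-hematological, non-metabolic, non-neuropathy toxicity, whether or not the patient continues, or (ii) failure to resume within 30 days of initial stopping for toxicity. Use that one clock in 4.1, 6.1, 6.4.1, Table 6-2 and 6.4.2. Keep the clinical-benefit exception in Tables 6-3 and 6.5 for treatment decisions only. Report the withdrawal rate alongside.

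The cost is a protocol amendment; toxicity is already graded by CTCAE, so grade IV events need no new data. The rule becomes somewhat stricter. At a true 15% qualifying rate with one third of grade IV cases otherwise retained:

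- If all events are grade IV, the counted rate rises from .15 × 2/3 = .10 to .15. The chance of stopping by 30 patients goes from .146 to .354 (looks every 5) or from .096 to .285 (every 10).
- If half are grade IV, the counted rate rises from .15 × 5/6 = .125 to .15. The chance goes from .241 to .354, or from .179 to .285.

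The 15% limit was set for withdrawals, so the sponsor should confirm that it still suits the combined event and, if it changes, recompute the boundaries and probabilities. Making withdrawal mandatory in 6.15 would also close the counting gap, but it would take away the option of continuing a patient who recovers and benefits.
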